6.2.2 Method of Detecting AEs, SAEs, and Other Reportable Safety Events

Care will be taken not to introduce bias when detecting AEs and/or SAEs and other reportable safety events. Open-ended and nonleading verbal questioning of the participant is the preferred method to inquire about AE occurrence.

6.2.3 Follow-up of AE, SAE, and Other Reportable Safety Event Information

After the initial AE/SAE report, the investigator is required to proactively follow each participant at subsequent visits/contacts. All AEs, SAEs, and other reportable safety events including pregnancy and exposure during breastfeeding, ECIs, cancer, and overdose will be followed until resolution, stabilization, until the event is otherwise explained, or the participant is lost to follow-up. In addition, the investigator will make every attempt to follow all non-serious AEs that occur in randomized participants for outcome. Further information on follow-up procedures is given in Appendix 5.

6.2.4 Sponsor Responsibility for Reporting Adverse Events

All AEs will be reported to regulatory authorities, IRB/IECs and investigators in accordance with all applicable country specific regulatory requirements, global laws and regulations.

6.2.5 Pregnancy and Exposure During Breastfeeding

Although pregnancy and infant exposure during breastfeeding are not considered AEs, any pregnancy or infant exposure during breastfeeding in a participant (spontaneously reported to the investigator or their designee) that occurs during the study are reportable to Merck.

All reported pregnancies must be followed to the completion/termination of the pregnancy. Pregnancy outcomes of spontaneous abortion, missed abortion, benign hydatidiform mole, blighted ovum, fetal death, intrauterine death, miscarriage, and stillbirth must be reported as serious events (Important Medical Events). If the pregnancy continues to term, the outcome (health of infant) must also be reported.

6.2.6 Events of Clinical Interest (ECIs)

Selected non-serious and SAEs are also known as ECIs and must be reported to Merck.

Events of clinical interest for this study include:

1. An overdose of pembrolizumab that is not associated with clinical symptoms or abnormal laboratory results. For purposes of this study, an overdose of pembrolizumab will be defined as any dose of 1,000 mg or greater (≥ 5 times the indicated dose). No specific information is available on the treatment of overdose of pembrolizumab. In the event of overdose, the participant should be observed closely for signs of toxicity. Appropriate supportive treatment should be provided if clinically indicated. If an adverse event(s) is associated with (“results from”) the overdose of a Merck product, the adverse event(s) is reported as a serious adverse event, even if no other seriousness criteria are met.
2. An elevated AST or ALT lab value that is greater than or equal to 3X the upper limit of normal and an elevated total bilirubin lab value that is greater than or equal to 2X the upper limit of normal and, at the same time, an alkaline phosphatase lab value that is less than 2X the upper limit of normal, as determined by way of protocol-specified laboratory testing or unscheduled laboratory testing.*

*Note: These criteria are based upon available regulatory guidance documents. The purpose of the criteria is to specify a threshold of abnormal hepatic tests that may require an additional evaluation for an underlying etiology.

There is currently no specific treatment in the event of overdose with olaparib and possible symptoms of overdose are not established.

Olaparib must only be used in accordance with the dosing recommendations in this protocol. Any dose or frequency of dosing that exceeds the dosing regimen specified in this protocol should be reported as an overdose.

Adverse reactions associated with overdose should be treated symptomatically and should be managed appropriately.

7.0 STATISTICAL ANALYSIS PLAN

7.1 Statistical Analysis Plan Summary

7.2 Statistical Analysis Plan

Sample size calculation: Single-Stage design will be used for this study [A'Hern, 2001; Fleming, 1982]. The study will require 48 subjects to decide whether the proportion responding (P), is less than or equal to 0.130 or greater than or equal to 0.280. If the number of responses is 10 or more, the hypothesis that $P \leq 0.130$ is rejected with a target error rate of 0.100 and an actual error rate of 0.087. If the number of responses is nine or less, the hypothesis that $P \geq 0.280$ is rejected with a target error rate of 0.100 and an actual error rate of 0.099.

Efficacy analyses: The iORR will be defined as the proportion of patients with an “immune” complete response (iCR) or “immune” partial response (iPR). For the primary iORR analysis in all the treated population, patients with an iCR or iPR will be counted as successes and all other patients (including those with missing response information) will be counted as failures. The percentage of iORR with its 95% confidence interval (CI) will be presented.

Progression free survival (PFS) will be defined among all treated patients as the time from first dose of study drug until the first date of either disease progression or death due to any cause. The date of disease progression will be defined as the earliest date of disease progression based on central review. For patients whose disease has not progressed at the time of the analysis, censoring will be performed using the date of the last valid disease assessment. The data will be analyzed by the Kaplan-Meier method. The median PFS time and 95% CI will be recorded.

Overall survival (OS): Median OS will be defined as the time from the beginning of study drug treatment until death due to any cause. For patients who have not died at the time of the analysis, censoring will be performed using the date the patient was last known to be alive. The data will be analyzed by the Kaplan-Meier method. The median OS and 95% CI will be recorded.

Safety analyses: Safety analyses will be presented descriptively. The focus of adverse event (AE) summarization will be on treatment-emergent adverse event (TEAEs). A TEAE is defined as an AE that occurs or worsens in the period extending from the first dose of study drug to 30 days after the last dose of study drug in this study. TEAEs will be summarized and summary tables will be created to show the number of patients reporting TEAEs by severity grade and corresponding percentages. A patient who reports multiple TEAEs within the same Preferred Term (or System Organ Class) is counted only once for that Preferred Term (or System Organ Class) using the worst severity grade. Separate summaries will be prepared for TEAEs classified as severe or life threatening (Grade 3 or higher); study drug-related AEs; AEs leading to treatment interruption, modification, or discontinuation; serious AEs; and death. Dose interruptions, reductions, and relative dose intensity will also be summarized.

All results including efficacy, PFS, OS and safety analysis will also be reported based on race/ethnicity stratification.

FATSI analysis will be conducted in batches. We expect that similar to mismatch repair deficient patients, the immune-related objective response will be at or above 40% in patients with functional FA deficiency (FATSI negative), and less than 10% in patients without either homologous recombination repair

deficiency or mismatch repair deficiency. Based on our prior screening data, we anticipate that close to 30% of patients will be FA functionally deficient.

Total enrollment of 48 patients is planned. We will report the 90% confidence interval estimates of iORR both overall and by FATSI status using the exact method (Clopper Pearson). However, the planned study is small for a well powered comparison given that we expect only 15 FATSI-negative patients. Instead, variation in iORR by FATSI status will be assessed by considering the one-sided 95% lower confidence limit (95%LCL) for the difference. As an example, an observed increase in iORR for FATSI- patients of 30.9%, based on 6 out of 15 FATSI- responders compared with 3 out of 33 FATSI+ responders, provides 95% confidence that the true increase for patients with FA deficient tumors is at least 7.1%, suggesting that further study of pembrolizumab/olaparib in FA deficient cervical cancer patients is warranted.

Kaplan-Meier curves will be used to estimate the distributions of overall survival and immune-related progression-free survival (iPFS). Point estimates and 2-sided 95% confidence intervals will be reported for selected times using Greenwood's variance and the log-log transform method. This will include the 20-week iPFS for purposes of comparison. Based on the panel sequencing results, somatic alterations will be summarized and reported as proportions for genes in FA competent and FA functionally deficient tumors. Confidence intervals will be calculated using the exact method. Additional analyses will be done to establish relationships between treatment and certain baseline characteristics, including deficiencies in the FA pathway, PD-L1 expression, TMB, other deficiencies in DNA damage repair mechanisms. These relationships will be explored primarily through logistic regression or cox proportional hazards regression, depending on the outcome of interest.

For known or predicted deleterious mutations of suspected inheritance trait detected during the trial, the process would be aided by making sure that patients carrying these mutations get referred for genetic counseling and CLIA certified germline analysis. The Miami Cancer Institute has these services readily available.

Stool Microbiome Data Analyses: Centered log-ratio (CLR) transformations will be applied to microbiome data. Log-ratios make the data symmetric and linearly related, and places the data in a log-ratio coordinate space. Thus, we can obtain information about the log-ratio abundances of features relative to other features in the compositional dataset. Zero counts of operational taxonomic units (OTU) will be converted to a probability vector prior to centered log-ratio transformation. Aitchison distance, which is simply the Euclidian distance between samples after CLR transformation, and the distances between samples same as the phylogenetic isometric log-ratio (ILR), will be calculated and used for clustering and ordination. Compositional principal component analysis (PCA) will be applied and biplots will be used to display the relationships between OTUs and the distances between samples.

Differential relative abundance will be based on the CLR values from a modelled probability distribution of the dataset, and the expected values of parametric and non-parametric statistical tests along with effect-size estimates will be reported. This approach reduces the false-positive identification problem to near 0 in real and modelled microbiome datasets with little effect of sensitivity to the negative correlation bias and is observed to be relatively insensitive to change when the data are subset.

Considering possible correlations among metabolites, penalized logistic model will be applied for selecting compositional components, which can predict the status of response to treatment and of treatment

related toxicity. The penalization coefficient λ is selected through leaving-one-out cross-validation. λ , which gives the smallest conditional likelihood deviance, will be used in final prediction.

Penalized survival models will be applied to investigate potential compositional components, which are associated with PFS. Similar to penalized logistic models, penalization hyperparameters will be selected through leaving-one-out cross-validation.

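### Does it matter that Section 7.2 names no method for the 95% interval on the primary iORR and also plans a 90% exact interval for the same rate?

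*Combined protocol and SAP*

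**What the plan says.** The sample size paragraph of Section 7.2 fixes the decision by a count. "Single-Stage design will be used for this study", with 48 patients, to decide whether the response proportion "is less than or equal to 0.130 or greater than or equal to 0.280". "If the number of responses is 10 or more", the lower hypothesis is rejected; with nine or fewer, the upper one is. Both target error rates are 0.100, and the actual rates are given as 0.087 and 0.099.

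The efficacy paragraph then defines the primary iORR in all treated patients, counting missing responses as failures, and says "The percentage of iORR with its 95% confidence interval (CI) will be presented". It names no method.

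The FATSI part of the same section says "We will report the 90% confidence interval estimates of iORR both overall and by FATSI status using the exact method (Clopper Pearson"). Further on, after the somatic-alteration proportions, it says "Confidence intervals will be calculated using the exact method".

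**The concern.** One quantity, the overall iORR, has two planned intervals at different levels, and neither is called the main one. Only the 90% interval has a method. Methods are given for lesser quantities (exact for the gene proportions, Greenwood with a log-log transform for survival at selected times), so the primary 95% interval stands out as the gap.

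In an open-label single-arm trial the data are visible as they accrue. With few responders, a method picked late could move the lower limit across the 13% reference rate. A reader could also meet a positive decision at 10 of 48 beside two intervals that contain 13%, with nothing in the plan to explain it. What would be at stake is the headline interval for the primary endpoint and how it is read.

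**Working it through.** **Inputs, all from Section 7.2:** n = 48, cut-off 10, p0 = 0.13, p1 = 0.28, and intervals at 95% (no method) and 90% (Clopper-Pearson).

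**1. The plan's own figures.** With X binomial:
- Type I error: P(X ≥ 10 | 48, 0.13) = 0.0865 (stated 0.087).
- Type II error: P(X ≤ 9 | 48, 0.28) = 1 − 0.9005 = 0.0995 (stated 0.099).

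Both agree with the plan to within rounding in the third decimal. A search over n shows that 48 with cut-off 10 is the smallest exact single-stage design meeting both 0.10 targets.

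**2. Intervals near the boundary.** Let x be the number of responders, p = x/48, and z the two-sided normal quantile (1.96 for 95%).
- Exact (Clopper-Pearson): lower limit is the α/2 quantile of Beta(x, n − x + 1); upper limit is the 1 − α/2 quantile of Beta(x + 1, n − x).
- Wilson: [p + z²/2n ± z√(p(1 − p)/n + z²/4n²)] / (1 + z²/n).
- Wald: p ± z√(p(1 − p)/n).

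| x | Exact 95% | Wilson 95% | Wald 95% | Exact 90% |
|---|---|---|---|---|
| 10 | 10.5–35.0% | 11.7–34.3% | 9.3–32.3% | 11.8–32.8% |
| 11 | 12.0–37.3% | 13.3–36.5% | 11.0–34.8% | 13.4–35.1% |
| 12 | 13.6–39.6% | 14.9–38.8% | 12.7–37.3% | 15.1–37.3% |

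The smallest count whose 95% lower limit exceeds 13% is 12 (exact), 11 (Wilson) or 13 (Wald, 14.5%).

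**3. How often the method changes the reading.** At a true rate of 28%:
- P(X = 10) = 0.9005 − 0.8271 = 0.0734.
- P(X = 11) = 0.0734 × (38/11) × (0.28/0.72) = 0.099.
- P(X = 12) = 0.099 × (37/12) × (0.28/0.72) = 0.118.

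Taking exact as the reference, Wilson differs only at 11 (9.9%) and Wald only at 12 (11.8%). The sum, 21.7%, mixes two separate disagreements. It describes the uncertainty only if all three methods are treated as equally open, and neither Wilson nor Wald appears in the documents.

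**4. The boundary at 10 of 48.** The rule is a one-sided test at a nominal 0.10. Its matching interval is therefore the two-sided 80% exact one. At 10/48 that interval has lower limit 13.4%, above 13%. At 9/48 its lower limit is 11.6%, below 13%, and its upper limit is 27.98%, just below 28%. It agrees with the rule on both sides of the cut-off. Intervals at 90% and 95% are wider by construction, so at 10/48 both exact intervals reach below 13%.

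**The case for a change.** The best case for a change is that a pre-specified plan should not leave the main interval for its primary endpoint to inference. The sentence on exact intervals after the gene proportions does not formally cover the iORR, and the Clopper-Pearson sentence is tied to the 90% level. Even if exact was meant for both, the two planned intervals part company at 11/48: the 90% lower limit is 13.4% and the 95% lower limit is 12.0%. Naming the method would therefore not by itself say which interval leads. A sentence or two would settle it at almost no cost.

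The textual point stands: the method is missing and the 90% overall interval has no label. The consequence does not stand. The plan never asks whether an interval excludes 13%; that test comes from outside the document. Placement also answers most of the question of which interval leads. The 95% interval directly follows the definition of the primary analysis and matches the level used for PFS and OS, while the 90% interval sits with the FATSI subgroups it accompanies. Both sentences can be followed as written without contradiction.

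**Conclusion.** No change to the plan follows. This is missing detail that an analyst would fill sensibly: an exact 95% interval as the main one, the exact 90% interval beside the FATSI results, and the count of 10 or more in 48 governing the conclusion. That choice fits the exact binomial design and the method named elsewhere in Section 7.2. The decision rule, the recomputed type I error of 0.0865 and the recomputed type II error of 0.0995 are the same under any interval method.

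The most that could shift is a descriptive reading against 13%, at one response count per alternative method: 11 for Wilson (9.9% at a true 28%) or 12 for Wald (11.8%). The positive decision at 10/48 beside intervals that contain 13% (probability 7.3% at a true 28%) reflects different confidence levels. Adding a one-sided 90% bound to match the rule would be a preference and would change no result.

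These figures assume exactly 48 treated patients and that exact is the intended method, which is an inference from the rest of the section.

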5.2 Trial Intervention(s)

The intervention(s) to be used in this trial is outlined below in Table 2

Table 2 Trial Intervention(s)

Drug	Dose/Potency	Dose Frequency	Route of Administration	Regimen/Treatment Period	Use
Pembrolizumab	200 mg	Q3W	IV infusion	Day 1 of each 3-week cycle	Experimental
Olaparib tablet	300 mg	Twice Daily	Oral	Daily	Experimental

Trial intervention(s) should begin as close as possible to the date on which intervention is assigned.

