5.8 Participant Replacement Strategy

We anticipate enrollment of 48 patients for which tumor and toxicity assessments following pembrolizumab/olaparib administration can be made. We will replace patients enrolled for which clinical trial discontinuation was performed prior to any administration of pembrolizumab or those for which pembrolizumab is discontinued due to acute hypersensitivity reactions during the first administration of pembrolizumab. An attempt will be made to assess tumor response in all enrolled patients as specified in the protocol. Patients experiencing clinical deterioration after two doses of pembrolizumab, will be considered treatment failures, will count as tumor progression, and will not be replaced.

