6.1.1.6.3 Subsequent Anti-Cancer Therapy Status

The investigator or qualified designee will review all new anti-neoplastic therapy initiated after the last dose of trial treatment. If a participant initiates a new anti-cancer therapy within 30 days after the last dose of trial treatment, the 30-day Safety Follow-up visit must occur before the first dose of the new therapy. Once new anti-cancer therapy has been initiated, the participant will move into survival follow-up.

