6.1.2.6.2 Tumor Imaging During the Study

The first on-study imaging assessment should be performed at 9 weeks (± 7 days) from the date of first dose. Subsequent tumor imaging should be performed every 9 weeks (± 7 days) or more frequently if clinically indicated. After 52 weeks (± 7 days), participants who remain on treatment will have imaging performed every 12 weeks (± 7 days). Imaging timing should follow calendar days and should not be

adjusted for delays in cycle starts. Imaging should continue to be performed until disease progression is identified by the Investigator.

Objective response should be confirmed by a repeat imaging assessment. Tumor imaging to confirm PR or CR should be performed at least 4 weeks after the first indication of a response is observed. Participants will then return to regular scheduled imaging every 9 weeks, starting with the next scheduled imaging time point. Participants who receive additional imaging for confirmation do not need to undergo the next scheduled tumor imaging if it is less than 4 weeks later; tumor imaging may resume at the subsequent scheduled imaging time point.

Per iRECIST (Section 7.1.2.6.6), disease progression should be confirmed by the site 4 to 8 weeks after first radiologic evidence of PD in clinically stable participants. Participants who have unconfirmed disease progression may continue on treatment at the discretion of the investigator until progression is confirmed by the site provided they have met the conditions detailed in Section 7.1.2.6.6. Participants who receive confirmatory imaging do not need to undergo the next scheduled tumor imaging if it is less than 4 weeks later; tumor imaging may resume at the 1.2.6.6.subsequent scheduled imaging time point, if clinically stable. Participants who have confirmed disease progression by iRECIST, as assessed by the site, will discontinue study treatment. Exceptions are detailed in Section 7.

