6.1.2.6.3 End of Treatment and Follow-up Tumor Imaging

In participants who discontinue study treatment, tumor imaging should be performed at the time of treatment discontinuation (± 4 week window). If previous imaging was obtained within 4 weeks prior to the date of discontinuation, then imaging at treatment discontinuation is not mandatory. In participants who discontinue study treatment due to documented disease progression and the investigator elects not to implement iRECIST, this is the final required tumor imaging.

For participants who discontinue study treatment without documented disease progression, every effort should be made to continue monitoring their disease status by tumor imaging using the same imaging schedule used while on treatment (every 9 weeks in Year 1 or every 12 weeks after Year 1) to monitor disease status until the start of a new anticancer treatment, disease progression, pregnancy, death, withdrawal of consent, or the end of the study, whichever occurs first.

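### Section 5.8 counts clinical deterioration as progression, but the PFS definition in 7.2 does not pick it up, so some of these patients may be censored or counted only at death

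*Combined protocol and SAP*

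**What the plan says.** Section 5.8 (Participant Replacement Strategy): "Patients experiencing clinical deterioration after two doses of pembrolizumab, will be considered treatment failures, will count as tumor progression, and will not be replaced". It names no date, no assessor and no endpoint.

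Section 7.2 (Efficacy analyses) runs PFS from first dose "until the first date of either disease progression or death due to any cause". On dating: "The date of disease progression will be defined as the earliest date of disease progression based on central review". For patients who have not progressed, "censoring will be performed using the date of the last valid disease assessment". It does not mention clinical deterioration or section 5.8. It does not say what happens to a patient whose only assessment is the screening scan. It also promises a 20-week iPFS estimate but gives iPFS no separate event or censoring rule.

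The timing comes from two other places. Table 2 in section 5.2 puts pembrolizumab on "Day 1 of each 3-week cycle", so dose 2 is at about week 3. Section 6.1.2.6.2 says: "The first on-study imaging assessment should be performed at 9 weeks (± 7 days) from the date of first dose".

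Several sections supply other scans. Section 6.1.2.6.3 asks for imaging at treatment discontinuation, within four weeks either way, and continued imaging if there is no documented progression. Section 6.1.2.6.2 allows earlier scans when clinically indicated, and 6.1.2.6 lets unscheduled images be used. Imaging ends with new therapy. Section 6.1.1.6.3: "Once new anti-cancer therapy has been initiated, the participant will move into survival follow-up".

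**The concern.** The two sections can give different answers for the same patient. Section 5.8 calls her progressed. Section 7.2 dates progression by central review, which has nothing to date if no scan shows it. An analyst working from 7.2 alone would censor her or wait for her death. An analyst who also applies 5.8 would count an event, on a date of his or her own choosing.

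Censoring of this kind is informative, because the patients affected are among the earliest to fail. The trial has no control arm, so nothing offsets the bias. Section 7.2 reports the 20-week iPFS for comparison purposes, and PFS is also the outcome of the penalized survival models planned for the microbiome data.

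**Working it through.** **1. The plan's own figure.** The documents state no PFS assumption, so the only design figure to reproduce is the iORR rule. Exact binomial, n = 48: P(X ≥ 10 | 0.13) = 0.0865 (stated 0.087) and P(X ≤ 9 | 0.28) = 0.0995 (stated 0.099). It reproduces. In the primary analysis every patient without iCR or iPR, including those with missing response, is already a failure, so this point does not touch that rule.

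**2. The two sections side by side.**

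| Patient who deteriorates after dose 2 | Section 5.8 | Section 7.2 taken alone |
|---|---|---|
| No scan after screening, alive at analysis | Progressed | Censored at the screening scan |
| No scan after screening, dies later | Progressed | Event at death |
| Later scans all short of progression, alive | Progressed | Censored at the last scan |
| Discontinuation scan shows progression on central review | Progressed | Event at that scan; little difference |

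In the first row the screening scan may be up to 21 days before allocation (6.1.2.6.1), while PFS starts at first dose. The censoring time is therefore zero in practice.

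**3. Size at 20 weeks.** All rates here are assumed. Let a share f deteriorate in weeks 3–9 with no later scan, and let S be 20-week PFS in the other patients.

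- (A) Event at deterioration: (1 − f) × S.
- (C) Censored at time zero: S. The ratio C/A is 1/(1 − f): 1.05 at f = 5%, 1.11 at 10%, 1.25 at 20%.
- (B) Event only at death: (1 − f) × S + f × q, where q is the chance of being alive at week 20.

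For S, take exponential progression with median m weeks and scans every 9 weeks. Progression is then seen by week 20 only if it occurs by week 18, so S = 2^(−18/m): 0.383 at m = 13 and 0.619 at m = 26. For q, take deterioration uniform over weeks 3–9 and a median of 8 weeks from then to death. Averaging 2^(−(20−u)/8) over u from 3 to 9 gives q = 0.30.

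| f | m = 13: A / B / C | m = 26: A / B / C |
|---|---|---|
| 5% | 0.364 / 0.379 / 0.383 | 0.588 / 0.603 / 0.619 |
| 10% | 0.345 / 0.375 / 0.383 | 0.557 / 0.587 / 0.619 |
| 20% | 0.306 / 0.367 / 0.383 | 0.495 / 0.555 / 0.619 |

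Counting only at death adds f × q: 1.5, 3.0 and 6.0 percentage points at f = 5%, 10% and 20%. If the median time to death is 4 weeks, q = 0.09 and the gain is 0.5 to 1.8 points over that range of f. If it is 16 weeks, q = 0.55 and the gain is 2.7 to 10.9 points.

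**4. Effect of the other scans.** If a share r of these patients gets a dated progression from another scan, f becomes f(1 − r). With f = 10% and r = one half (assumed), f falls to 5% and the factor from 1.11 to 1.05.

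**5. Median.** At m = 13 and f = 10%, the proportion with an event by week 9 under A is 0.10 + 0.90 × (1 − 0.619) = 0.443, and by week 18 it is 0.655. The median reads 18 weeks, as it does under C (0.381 and 0.617). At m = 26 it is 27 weeks under both. At f = 20% the proportion under A just passes one half one scan earlier (0.505).

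**The case against.** The strongest reply is that 7.2 censors only patients who have not progressed, and 5.8, in the same document, says these patients have. Read together, 5.8 supplies the event. That reading is fair, and it means the documents do not show that such patients will be censored. It does not settle the analysis, because 5.8 gives no date or assessor and 7.2 asks for a central-review date.

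The second reply is that the other scans and the recording of deaths leave few patients in the gap. Deterioration alone does not trigger survival follow-up, and censoring at baseline needs no later scan of any kind and no recorded death. This stands as a limit on size. The gap still remains:

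- The discontinuation scan is waived if imaging was done in the previous four weeks. A screening scan within a week before first dose can meet that for a patient stopping at week 3.
- A scan short of progression gives no event.
- Disease imaging ends at new therapy.
- Sections 5.6 and 6.1.5.3.2 reserve follow-up imaging for patients who stop for reasons other than progression. A patient recorded as progressed under 5.8 may get none.
- A death recorded later gives an event, but a late one.

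A reader might also infer two stronger points. One is that median PFS would be overstated by a whole scan interval. That appears when the assumed median falls on a scan week, such as a true median of 9 weeks, or when the event proportion sits almost exactly at one half, as at f = 20% above. The documents give no basis for assuming either. The other is that 5.8, having no upper time limit, turns an earlier responder into a failure. Section 7.2 counts any iCR or iPR as a success, and nothing in 5.8 withdraws a documented response.

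**Conclusion.** The point holds as an unreconciled conflict between 5.8 and 7.2. Where a patient deteriorates without imaging-documented progression and 7.2 is applied literally, PFS is biased upward. The 20-week iPFS is biased in the same way, if it follows the PFS rule (an assumption, since 7.2 does not define it).

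The size is unknown because the documents give no rate of such deterioration. With 5% to 10% of patients censored at baseline, 20-week PFS is inflated by a factor of about 1.05 to 1.11. That is 2 to 4 percentage points if the other patients' median is 13 weeks, and 3 to 6 points if it is 26 weeks. The share, the medians and the exponential form are all assumed, and scans that catch some of these patients reduce the effect in proportion. The median may not move. The sample size, the 10-of-48 rule and the primary iORR do not change. It should be settled before analysis, but it does not threaten the main conclusion.

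**What to change.** In section 7.2:

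1. State that clinical deterioration under 5.8 is a PFS event on the date the investigator documents it, when no earlier central-review progression date exists. This reconciles the two sources of date.
2. State the rule for patients with no post-baseline assessment. For example, those with neither a 5.8 event nor a recorded death are censored on the day of first dose.
3. State that iPFS uses the same two rules, or give its own.
4. Report PFS by centrally reviewed progression or death only as a sensitivity analysis, with the number of patients whose status or date differs.

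Section 5.8 needs only a cross-reference to 7.2. The case report form needs a dated entry for the deterioration.

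The cost is a few sentences and one extra Kaplan-Meier run. The main drawback is that some investigator judgement enters PFS in an open-label trial; the sensitivity analysis shows how much depends on it. Reported PFS may be slightly less favourable. No treatment rule changes.
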